**Fig. 8. “Go” criteria: #1, plus at least one of #’s 2, 3 & 4 ( $d > 0.5$ )**

1. **Target engagement:** APS learning, AMPH > PBO,  $p < 0.05$
2. **Greater clinical, neurocognitive or functional gains:**
  - $\downarrow$ PANSSt,  $\uparrow$ MCCB-C or  $\uparrow$ Fnxn: AMPH+TCT > PBO+TCT
3. **Faster clinical, neurocognitive or functional gains:**
  - drug group x session interaction ( $p < 0.05$ ) followed by AMPH+TCT > PBO+TCT at specific session # or combination;
4. **More durable** clinical, neurocognitive or functional gains:
  - AMPH+TCT > PBO+TCT at post-TCT week 12.

PANSSt: Positive & Negative Symptom Scale total; MCCB-C: MATRICS Composite; Fnxn: Function (assessed via the World Health Organization Disability Schedule 2.0 (WHODAS))

**Outcome and “Go Decisions”.** In addition to confirming “target engagement”, this application tests the hypothesis that SZ patients given AMPH +TCT will exhibit greater, faster and/or more durable improvements (change from baseline) in symptoms, neurocognition and/or function compared to patients given PBO+TCT, and that this enhanced clinical response will be associated with greater AMPH-enhanced TCT learning.

The small “n” necessitated by the 3-year timeline and demanding treatment schedule greatly constrains the total number of outcome measures.

Moreover, the plan to assess not only magnitude but also rate and durability of PACT gains triples the number of primary analyses. Thus, we selected only one **primary** clinical, neurocognitive and functional outcome measure (Fig. 8) – recognizing that they are relatively “blunt” metrics - but will track several other, more focused, measures as well as inter-measure correlations in exploratory analyses to inform future studies.

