A “Go” decision requires: 1) confirmation of target engagement (APS learning, AMPH>PBO,  $p < 0.05$ ); 2) evidence of gains from PACT ( $d \geq 0.5$  (AMPH > PBO)) in primary clinical, neurocognitive and/or functional measures (Fig. 8), and 3) the absence of adverse effects of AMPH that are significantly greater than PBO levels. The decision to not use traditional statistical significance as “Go” criteria for Aim 2 reflects this RFA’s call for “Pilot” studies, the need to identify candidate treatments for a subsequent larger “n” Confirmatory Efficacy R01 study, and the limits in sample size resulting from the 3-year R33 duration. Cohen defined a medium effect size ( $d=0.5$ ) as one that is “visible to the naked eye,” and this amount of change is viewed as clinically meaningful in trials targeting negative symptoms. This  $d=0.5$  “Go” threshold for Aim 2 corresponds to a “number needed to treat” (NNT) value  $\approx 3.62$ . While a “Go” decision does not require identification of a biomarker predicting greater PACT

sensitivity (Aim 3), the identification of one or more meaningful predictors that could be incorporated into a Confirmatory Efficacy trial would favorably impact a “Go” decision.

Staff assessing outcome measures are blind to treatment arm, and for some measures receive training using videotaped and practice interviews until achieving high (ICC>.80) reliability based on 20 assessments by 2 raters. We achieve high inter-rater reliability (e.g., ICC>0.85 for PANSS total), and check for rater drift each 90d.

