**Aim 2 – Test clinical, neurocognitive and functional impact of AMPH on TCT, and its relationship to target engagement:** We will determine if AMPH+TCT produces greater, faster or more durable clinical, neurocognitive or functional gains from baseline, compared to PBO+TCT, over a 30-session course of TCT. A Cohen’s  $d \geq 0.5$  for the main effect of drug (PBO vs. AMPH) or drug x session (#10, 20, 30) interaction in an LME model is the primary “Go” criteria. The main effect of drug assesses “greater” gains. Reverse Helmert contrasts for session assesses “faster” gains. A separate model comparing differences in outcomes at 12-weeks post-TCT assesses “more durable” gains. Secondary regression analyses will examine whether change in AMPH-enhanced APS learning (“within-subject” target engagement; Aim 1) predicts gains in Aim 2 outcome measures.

**Aim 3 – Biomarkers of AMPH-induced gains:** We will determine if baseline levels of specific neurocognitive or EEG-based measures, or changes in specific measures with initial AMPH exposure (Test 2 vs. 1), predict greater sensitivity to AMPH-enhanced neurocognitive, clinical or functional gains over 30-h of TCT. Regression analyses will assess whether specific candidate biomarkers predict AMPH-enhanced gains in outcome measures.

**Subject “throughput”:** We will enroll and screen 23 subjects/yr, test target engagement in 18 subjects/yr, and (conservatively) complete TCT training in 12 subjects/yr. This will yield 2 “target engagement” Aim 1 arms of  $n=27$ , and (conservatively) 2 TCT completion Aim 2 arms of  $n=18$ . Training capacity (2 TCT stations with morning and afternoon sessions on M, W and F, with T and Th “make-up” days for missed appointments, 48 weeks/year) allows for a “maximum throughput” of 19.2 subjects/yr. To reach the target of **12 TCT-completing subjects /year**, we would need to maintain training rates of **62.5% capacity**. This is well within our historical testing levels.

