General Statistical Approach: Hypothesis tests are 2-sided ($\alpha=.05$). Type I error is controlled by selecting optimal *a priori* targets for primary analyses; secondary analyses use false discovery rate corrections. When appropriate, missing data are handled via multiple imputation or full information maximum likelihood estimation. Expected drop-out rates and ways to minimize them are described in the parent application.

Differential drop-out rates from PBO vs. AMPH arms are monitored. Clinical follow-up is pursued with all patients exiting the study through post-TCT week 12.

Cohort differences: For between-subject contrasts (drug), baseline demographic, clinical, antipsychotic/anticholinergic load and performance differences are tested and used as covariates if indicated. Sex differences are tested for all measures.

Procedures for Alternative or Unexpected Results: Linear mixed-effects models allow for the analysis of all available data using an intent-to-treat approach. This approach, however, assumes that data are missing at random. A potential concern is nonrandom dropout, particularly when dropout is related to the (missing) outcomes; that is, not missing at random. To make the missing at random assumption more plausible, we will explore the use of auxiliary variables. Auxiliary variables are covariates that predict both dropout and outcomes. By adding auxiliary variables to our models, nonrandom dropout is corrected by conditioning treatment effects on the predictors of dropout.

Primary Efficacy Endpoint(s): Aim 1: Target engagement – APS learning will be significantly greater under AMPH vs. PBO conditions. Aim 2: Pilot trial - Compared to PBO arm patients, AMPH arm patients will exhibit greater clinical benefit, as indicated by one or more of the following: greater, faster or more durable improvements in PANSSt (reduced scores; see below, “Go/No-Go”), MCCBc (increased scores) or WHODAS (reduced scores).

Secondary Efficacy Endpoint(s): Aim 3: Biomarkers - baseline levels of specific neurocognitive or EEG-based measures, or changes in specific measures with initial AMPH exposure, predict greater sensitivity to AMPH-enhanced neurocognitive, clinical or functional gains over 30 sessions of TCT.

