Analyses testing primary and secondary hypotheses will include all subjects' clinical, neurocognitive and functional assessments. Data from subjects who do not complete the full study are carried forward in an "intent to treat" design, and their data are analyzed using linear mixed models. Separate analyses will compare completion / drop-out rates across arms, as well as a 14-item 7-point Likert scale assessing treatment satisfaction.

Go/No-Go decision and primary and secondary endpoints

"Go/No-Go" decisions are based on traditional statistical significance (Aim 1) and effect sizes (Aim 2). Formal statistical testing is conducted using linear mixed-effects (LME) models; hypothesis tests are 2-sided ($\alpha=.05$). Model parameters are estimated via the R lme4 package and Cohen's d is estimated via the EMATools package. Type I errors are minimized by constraining the number of primary analyses; secondary analyses use false discovery rate corrections.

PANSSt scores will be assessed at specific intervals. **It is important to emphasize that the anticipated symptomatic gains will reflect an enhanced impact of TCT, rather than a direct therapeutic impact of AMPH (5 mg, 2-3 times per week).** Because TCT is associated with improvements in both positive and negative symptoms, our *a priori* hypothesis is that a PACT effect will be evident in both positive and negative symptoms. Hence, PANSSt is used as the primary metric of symptomatic gains. A greater reduction in PANSSt score will be detected using data from baseline through TCT 30h, by a significant main effect of group (arm) or a significant interaction of group x session, with post-hoc contrasts revealing significant group differences at TCT 30h. A faster reduction in PANSSt scores will be detected using these same data by a significant interaction of group x session and a significant group difference at a point prior to TCT 30h. A more durable reduction in PANSSt scores will be detected using data from TCT 30h through 12 weeks post-TCT, by a significant main effect of arm or a significant interaction of group x post-TCT day, with post-hoc contrasts revealing significant group differences 12 weeks post-TCT.

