Comparable analytic approaches will be used for neurocognition (MCCBc) and function (WHODAS) as described in "Research Strategy". Data will be described as means with SEM. Tests for normalcy will be applied to all data and non-parametric comparisons will be used if normalcy is not demonstrated. The Analysis Set for these data will be all subjects who have completed 30h of TCT and post-TCT clinical, neurocognitive and function assessments. When appropriate, missing data are handled via multiple imputation or full information maximum likelihood estimation.

Secondary regression analyses assess the predictive value of putative biomarkers on clinical, neurocognitive or functional gains from the addition of AMPH to TCT. Future studies with larger samples will assess potentially more informative models, e.g. Path Analysis to study moderating effects of APS AMPH sensitivity and biomarkers on both indirect (moderated-mediation) and direct paths between treatment and outcome.

Power analyses

Consistent with the FOA, this study will adequately power tests of target engagement (Aim 1) for traditional significance, while the "Go" signal for therapeutic impact (Aim 2) is based on effect size ($d=0.5$). To detect target engagement with $d=0.5$, 80% power, $\alpha=0.05$, test-retest correlation =0.8, and a linear treatment effect, $n=27$ randomized participants are required per group. This is a very conservative estimate of d for target engagement, since empirically, d for target engagement with 5 mg amphetamine was 0.85 (Fig. 3A). A future Confirmatory Efficacy trial will be powered to apply more robust approaches to Aim 2, e.g. Path Analysis¹⁰⁸ to study moderating effects of APS AMPH sensitivity and biomarkers on both indirect (moderated-mediation) and direct paths between treatment and outcome.

Project Modification: Statistical Analysis Plan

The original study design included separate, parallel assessments of amphetamine (AMPH) (vs. placebo (PBO)) and memantine (MEM) (vs. PBO) effects on TCT-associated clinical, neurocognitive and functional gains. However, these designs pre-dated the pandemic, and between the date that they were proposed (10/2019) and the project start date (8/2020), our institution implemented a pandemic-related shut-down of clinical research activities. Even with the gradual resumption of research activities, recruitment lagged significantly behind target levels. As a result, we made several pragmatic adjustments to the original study designs:

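### The Aim 2 Go decision is said to rest on effect size, but Fig. 8 item 3 and the SAP's definitions of greater, faster and more durable gains require statistical significance

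*SAP*

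**What the plan says.** **Effect size as the Go basis.** The protocol's section on outcome and Go decisions requires d>=0.5 in a primary clinical, neurocognitive or functional measure. It explains the choice in a sentence that begins "The decision to not use traditional statistical significance as" and goes on to cite the pilot setting and limited sample size. The protocol's Data Analysis text for Aim 2 makes d>=0.5 the primary Go criterion, "for the main effect of drug (PBO vs. AMPH) or drug x session (#10, 20, 30) interaction in an LME model". The opening of Data Analysis, the first sentence of the SAP's Go/No-Go section, and both Power analyses sections also tie the Aim 2 Go to effect size.

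**Significance in the same place.** Fig. 8 of the protocol lists the Go criteria as item 1 (target engagement) plus at least one of items 2, 3 and 4, at d>0.5. Item 3, faster gains, first requires a drug-by-session interaction at p<0.05, "followed by AMPH+TCT > PBO+TCT at specific session # or combination". Items 2 and 4 have no p-value condition.

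After its opening sentence, the SAP's Go/No-Go section says a greater PANSS total reduction will be detected "by a significant main effect of group (arm) or a significant interaction of group x session", with significant contrasts at 30 hours. Faster and more durable reductions are defined in the same way, and no value of d appears in any of the three definitions. The SAP's list of primary endpoints refers the reader to this section for Aim 2, and a following sentence extends the approach to the MCCB composite and WHODAS.

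**The Project Modification.** It describes mixed-model tests at alpha 0.05, a between-group d with no cut-off, and a within-group threshold: d in the active group at least 0.4 above d in the placebo group. It restates no Go rule.

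**The concern.** The Go/No-Go decision is the main product of this pilot, and the protocol promises clear criteria for it. A p-value condition inside a rule that is said not to use significance is a contradiction. Defining the endpoint by significance, in the section that sets out the Go decision, leaves unclear whether those tests decide anything. The protocol itself concedes, under its sixth limitation, that the sample is too small to reach conventional significance easily, so the choice of criterion can matter. If it stays open, the deciding criterion can be chosen once the results are known.

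**Working it through.** **1. The plan's own figure.** The SAP's Power analyses section gives a calculation for Aim 1 only: "To detect target engagement with $d=0.5$, 80% power", alpha 0.05, "test-retest correlation =0.8, and a linear treatment effect", leading to 27 per group. "Hypothesis tests are 2-sided" at alpha 0.05.

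- SD of a change score, in raw-score SD units: sqrt(2 × (1 − 0.8)) = 0.632, variance 0.40.
- Normal approximation: n = 2 × (1.960 + 0.842)² × 0.40 / 0.5² = 25.1, so 26 per group.
- Noncentral t: 27 per group, power 81.3%.

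The figure of 27 reproduces with d on the raw-score scale. No sample size or power is stated for Aim 2.

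**2. Smallest significant d, with d scaled by the SD of the analysed score.** The inputs are 18 completers per arm (protocol, Recruitment and Retention Plan) and 27 randomised per arm. A single two-arm contrast stands in for the mixed model.

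Smallest significant d = t(0.975, 2n − 2) × sqrt(2/n); t at d=0.5 is 0.5 × sqrt(n/2).

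| n per arm | t at d=0.5 | p at d=0.5 | Smallest significant d |
|---|---|---|---|
| 18 | 0.5 × 3 = 1.50, 34 df | 0.143 | 2.032 / 3 = 0.68 |
| 27 | 0.5 × 3.674 = 1.84, 52 df | 0.072 | 2.007 / 3.674 = 0.55 |

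The criteria disagree for observed d from 0.50 up to 0.68, or up to 0.55. Above and below that band they agree. The band closes at about 32 per arm.

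**3. How often one contrast falls in the band.** For true effect δ, the observed contrast follows a noncentral t with noncentrality δ × sqrt(n/2).

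| n per arm | True d | P(observed d>=0.5) | P(significant, favouring AMPH) | Difference |
|---|---|---|---|---|
| 18 | 0.5 | 50.4% | 30.8% | 19.7% |
| 18 | 0 | 7.1% | 2.5% | 4.6% |
| 27 | 0.5 | 50.3% | 43.8% | 6.6% |
| 27 | 0 | 3.6% | 2.5% | 1.1% |

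Differences are taken before rounding.

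**4. The same check with d scaled by the raw-score SD.** The original rule leaves the computation of d to a software package and does not name the SD. If d uses the raw-score SD and the test is on change scores, the cut-off is multiplied by sqrt(2 × (1 − r)). The correlation r is given for Aim 1 only, so its use for Aim 2 is an assumption.

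| Assumed r | Smallest significant d, 18 per arm |
|---|---|
| 0.5 | 0.68 |
| 0.6 | 0.61 |
| 0.7 | 0.53 |
| 0.8 | 0.677 × 0.632 = 0.43 |
| 0.9 | 0.30 |

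At r=0.8, observed d from 0.43 to just under 0.50 is significant but fails d>=0.5, which is the opposite direction from step 2.

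**5. Fig. 8 against the Aim 2 analysis text.** Take an interaction effect with d>=0.5 and p>0.05. The Aim 2 text counts it towards Go; Fig. 8 item 3 does not. No assumption about scaling is needed to see this conflict.

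**The case against.** The best defence is that the documents do name a governing rule. Five places say effect size decides Aim 2, including the sentence that opens the SAP section in question, and the protocol argues for that choice. The SAP heading also covers primary and secondary endpoints, so the significance wording can be read as describing formal endpoint tests; that paragraph never says that they decide Go. Much of this stands. A reader might infer that Aim 2 has two equal Go rules and that the same data generally give opposite answers. The documents do not support that: significance enters a stated Go rule explicitly only in Fig. 8 item 3, and elsewhere only by implication.

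The Fig. 8 conflict is also narrow. Any one of items 2 to 4 suffices alongside item 1, so the p-value condition changes Fig. 8's result only when faster gains are the sole route.

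A reader might also take 50% and 31% as Go probabilities. They are not. The full rule spans three outcomes and three routes, and also requires target engagement and no significant excess of adverse effects. Nor do 18 or 27 per arm describe the modified study, which has three groups, pooled placebo, 2:1 allocation and samples reported as well below target.

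The defence does not explain Fig. 8 item 3. Nor does it say why the SAP's endpoint list points to definitions without any d in them.

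**Conclusion.** The concern holds as an internal conflict to be reconciled. Effect size is the stated Aim 2 Go basis; Fig. 8 item 3 contradicts it directly, and the SAP's definitions leave the role of significance ambiguous for all three primary outcomes.

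The disagreement is confined to a band next to the 0.5 threshold. The width and direction of that band depend on the SD used for d, which the plan does not state, so it cannot be said in general that one criterion is the more lenient. The sizes shown rest on a single two-arm contrast at the sample sizes planned before the modification. Numbers after the modification are not given; smaller samples would widen the band on the analysed-score scale.

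The Project Modification does not resolve the matter, because its 0.4 threshold is a within-group comparison and is not linked to the Go decision.

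**What to change.** 1. Remove p<0.05 from Fig. 8 item 3, so that it agrees with the protocol's Go decision text and Aim 2 analysis.
2. In the SAP's Go/No-Go section, define greater, faster and more durable by d>=0.5 with a 95% CI, label the significance tests as supportive, and apply this to PANSS total, MCCB composite and WHODAS.
3. Align d>0.5 in Fig. 8 with d>=0.5 in the rest of the protocol.
4. State which SD standardises d and which contrast it refers to, including which session contrast must reach the threshold for faster gains.
5. State whether the Project Modification's threshold, d(active) >= d(PBO) + 0.4, replaces d>=0.5 for the Go decision.
6. The modification is written as work already done, so an edit now cannot serve as pre-specification. Report the Aim 2 result under both the effect-size and the significance criteria, and disclose when the deciding one was fixed.

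Items 1 to 5 cost only wording in the protocol and SAP. Item 6 adds some reporting and no new data.

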## Recruitment and Retention Plan

We anticipate that over the course of this study we will consent 69 SZ individuals for screening, from whom we will advance 54 individuals to in-laboratory baseline testing and randomization into two arms with n=27 per arm. After study attrition, we conservatively expect that 36 individuals will complete 30 hours of TCT and longitudinal (12 week post-TCT) testing, and that attrition will be roughly balanced to arrive completed samples of n=18 per study arm.

Example of CONSORT Diagram of proposed R33 study

\* Conservative estimate of final n=18/arm for Aim 2 analyses

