Indirect indicators of clinical impact included subject attrition, C-SSRS responses, treatment satisfaction and adverse events (AEs). AMPH group subjects were evaluated for abnormal involuntary movements (AIMS) and for deleterious effects of AMPH cessation (AMPH Cessation Symptom Assessment). Analyses included non-parametric (Chi-Square) and parametric (rmANOVA) tests.

Linear mixed-effects models for outcome measures included all subjects who were randomized; df were estimated using the Satterthwaite approximation. Between- and within-group effect sizes for clinical, neurocognitive and functional measures were calculated based on all subjects who completed 30 TCT visits and P30 testing (“completers”). For all analyses, α was set at 0.05; for analyses of the 5 secondary outcome measures, findings were also evaluated with a more restrictive alpha level (0.01) to correct for multiple comparisons.

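### An unspecified normality test on all data can move the Aim 2 primary outcomes from the mixed model to a non-parametric comparison that does not supply the Go statistic, and the later modification does not withdraw the rule

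*SAP*

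**What the plan says.** The SAP section *Go/No-Go decision and primary and secondary endpoints* sets the main method: "Formal statistical testing is conducted using linear mixed-effects (LME) models". It defines greater, faster and more durable PANSS total gains through arm effects and arm by session interactions, takes Cohen's d from an R package, and extends the approach to the MCCB composite and WHODAS. The paragraph making that extension then adds: "Tests for normalcy will be applied to all data and non-parametric comparisons will be used if normalcy is not demonstrated". Its next sentences limit the analysis set to patients who completed 30 h of TCT and the post-TCT assessments, and allow multiple imputation or full-information maximum likelihood.

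The protocol (*Data Analysis*, Aim 2) makes the primary Go criterion a Cohen's d of at least 0.5 for the drug effect or the drug by session interaction in an LME, and assesses faster gains by reverse Helmert contrasts. Protocol Fig. 8 also asks for an interaction p-value below 0.05 for faster gains.

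The SAP's *Procedures for Alternative or Unexpected Results* gives the reason for choosing the model: "Linear mixed-effects models allow for the analysis of all available data using an intent-to-treat approach".

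The later *Project Modification: Statistical Analysis Plan* says the planned analyses were adjusted. It treats the outcomes as continuous, fits LMEs to all randomised subjects and computes effect sizes in completers. It mentions no normality rule. Its only reference to non-parametric tests is to Chi-Square tests, in the paragraph on attrition, suicidality, satisfaction and adverse events.

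**The concern.** The rule is mandatory in wording, yet leaves open which normality test is used and at what level. It does not say whether raw scores, changes or residuals are tested, whether by arm or pooled, how many failures count, or which comparison replaces the model.

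It also aims at the wrong object. An LME needs approximately normal residuals and random effects; raw scores at a visit can be non-normal without harming it, and the reverse can also occur. Failing to reject normality in a small sample does not demonstrate it either.

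What is at stake is the decision rule more than the error rate. The Go decision is written in terms of LME quantities. If one primary outcome switches, the plan does not say how d or the interaction is then obtained, and the three outcomes would enter a single Go rule on different footings. The choice would be made after seeing the data.

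**Working it through.** **1. The plan's own figure.** The documents give no figure for how often the switch would fire. The nearest is the Aim 1 sample size: "test-retest correlation =0.8, and a linear treatment effect, $n=27$ randomized participants are required per group", with d = 0.5, 80% power and two-sided α = 0.05. On change scores the variance is 2(1 − 0.8) = 0.4, so n = 2(1.960 + 0.842)² × 0.4 / 0.5² = 25.1, or 26 by the normal approximation. With the noncentral t, power is 79.8% at 26 and 81.35% at 27, so 27 reproduces. It serves below only as an arm size, with the protocol's completer forecast (*Recruitment and Retention Plan*): "attrition will be roughly balanced to arrive completed samples of n=18 per study arm".

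**2. What the Go rule needs against what a rank comparison gives.**

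| Needed | Source | From an ordinary two-group rank test |
|---|---|---|
| d for drug effect from an LME | Protocol, Aim 2 | No |
| d or p for drug by session | Protocol, Aim 2 and Fig. 8; SAP Go/No-Go section | No |
| Helmert contrasts over sessions | Protocol, Aim 2 | No |

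**3. Chance triggering.** Inputs: 3 primary outcomes (SAP, Project Modification); 5 time points, being baseline, sessions 10, 20 and 30, and 12 weeks after TCT (SAP, Design); 2 arms. The level for the normality tests is not stated, so 0.05 is assumed; the modification says "For all analyses, α was set at 0.05", without mentioning such tests. For k independent tests on normal data, P(at least one failure) = 1 − 0.95^k. Visits are correlated, so Shapiro–Wilk tests were also simulated (correlation 0.8 between visits, outcomes independent, 1,500 runs). The chance that at least one of the three outcomes fails is:

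| Layout | k | Formula | 18 per arm | 27 per arm |
|---|---|---|---|---|
| One pooled test per outcome | 3 | 14.3% | 13.9% | 16.1% |
| One test per arm per outcome | 6 | 26.5% | 25.9% | 25.8% |
| Pooled, 5 time points | 15 | 53.7% | 48.8% | 48.2% |
| Per arm, 5 time points | 30 | 78.5% | 73.6% | 72.9% |

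A single test fails 5% of the time. For one outcome alone the figure is about 10% (one test per arm) to 36% (per arm, 5 time points). Positively correlated outcomes would lower the any-of-three figures.

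**4. Consequences when it fires.** A simplified version was simulated: one follow-up, no missing data, Shapiro–Wilk on change scores in each arm at 0.05, then a t-test or a Mann–Whitney test on change (4,000 runs). The t-test and ANCOVA stand in for the LME. Skewed data are gamma with shape 4, an assumption. Power is at d = 0.5.

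| Data, n per arm | Fires | Type I, two-stage | ANCOVA | t on change | Two-stage | Mann–Whitney, change | Mann–Whitney, post score |
|---|---|---|---|---|---|---|---|
| Normal, 18 | about 10% | 5.6% | 66.2% | 62.9% | 63.0% | 59.4% | 28.6% |
| Normal, 27 | 9–10% | 5.2% | 84.4% | 82.2% | 82.1% | 79.2% | 40.9% |
| Skewed, 18 | 35–37% | 5.3% | 67.0% | 63.6% | 67.2% | 66.2% | 31.2% |
| Skewed, 27 | 49% | 4.9% | 84.9% | 81.8% | 84.8% | 84.8% | 45.2% |

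The simulation standard error at 5% is √(0.05 × 0.95 / 4,000) = 0.34 points, so the Type I results are compatible with 5%. Two things follow. Power is materially lost only if the replacement drops baseline (40.9% against 79.2% on normal data at 27 per arm). And the same skew fires the rule more often at 27 per arm than at 18, although the two-stage Type I error was 4.9% and 5.3%: firing tracks sample size, not need.

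**The case against.** The strongest reply is that the sentence is superseded in practice. The Project Modification says the analyses were adjusted and reports LMEs on all randomised subjects for these outcomes, which is much of what the fix asks for. That stands as evidence of what was done. It does not settle the plan: the modification neither withdraws the rule nor says whether normality was tested.

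Second, nothing makes d conditional on a normality test. The LME might still be fitted for d while only the post-hoc comparisons turn non-parametric, and the modification has a formula for d from change scores. That reading is possible, but the SAP does not state it, and a change-score d among completers is not the LME effect in the protocol's Go rule.

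Three stronger readings are tempting, and the documents do not support them:

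- A reader might infer that the switch will often fire by chance, at 79%. That needs 30 independent tests and a rule that any one failure counts. The SAP specifies neither, and its own power section assumes a test-retest correlation of 0.8.
- A reader might infer that the rule discards covariates and missing-data handling and so forfeits the all-randomised analysis. The replacement test is not named, baseline can be kept through change scores, and multiple imputation can accompany rank tests. In that paragraph non-completers are already excluded by the analysis-set definition, which is a separate matter.
- A reader might infer an inflated false-positive rate. The simulation shows none of any consequence.

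**Conclusion.** The point holds as a minor defect of specification. The October 2019 plan lets unspecified normality tests of the wrong quantity choose the method for the three Aim 2 primary outcomes, and the alternative does not ordinarily yield the statistics on which the Go rule rests. The chance of a needless switch in at least one outcome cannot be fixed from the documents. It is 5% for a single test, about 14% with one pooled test per outcome, and about 73% if every outcome, visit and arm is tested. These figures assume Shapiro–Wilk at 0.05, exactly normal data, two equal arms of 18 or 27, visits correlated at 0.8 and independent outcomes. The 2:1 allocation and pooled-placebo design were not modelled, because the SAP does not give the final group sizes.

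Type I error is not materially affected, and power loss is small unless baseline is dropped. Nothing in the documents shows that the analysis described in the modification was altered by this rule; the gap is that a reader cannot tell whether it still applied.

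**What to change.** Delete the normality sentence, or state in the Project Modification that it is withdrawn and when. Also record whether normality tests were run and whether any outcome was switched because of them. In its place, specify:

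- The LME is the primary analysis for PANSS total, MCCB composite and WHODAS, whatever any normality test shows.
- Residuals and estimated random effects are inspected graphically and reported.
- As a sensitivity analysis for each primary outcome, either bootstrap confidence intervals for the arm effect from the same model, resampling whole participants within arm, or a permutation p-value for that effect, permuting arm labels within the randomisation strata and separately for the 1:1 and 2:1 allocation periods.

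This keeps one method across the three outcomes and leaves the Go statistic defined. It costs a few lines of SAP wording and one short run, with no new data and no change to trial conduct.
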